4. ABSTRACT

Rationale and background: The Nordic countries, Denmark, Finland, and Sweden, provide a unique setting for the study of influenza vaccine effectiveness (IVE). The ubiquitous nationwide demographic and health registers, including vaccination and surveillance data, allow for large study cohorts with near real-time data availability. Seasonal influenza remains a major public health concern, particularly for vulnerable populations such as older adults and individuals at high-risk of serious influenza outcomes. While vaccination is the primary prevention strategy, its effectiveness varies across seasons, virus subtypes, and populations. Data on timely brand-specific IVE are limited.

Research question and objectives: The aim of this project is to evaluate the brand-specific effectiveness of seasonal influenza vaccines in preventing laboratory-confirmed and influenza-related outcomes during the 2024-2025 season in key target populations in Denmark, Finland, and Sweden.

Study objective:

- To provide timely estimates of brand-specific seasonal IVE against laboratory-confirmed and influenza-related outcomes for the 2024-2025 season.

Study design: Nationwide register-based cohort analyses in Denmark, Finland, and Sweden, during the study period from 1 October 2024 until the latest available date in 2025 at time of analyses (e.g., 1 March 2025). We will employ a matched cohort design, utilizing national registers to capture vaccination status, influenza outcomes, and relevant covariates. The study will focus on individuals aged 65 years and older, and adults at high risk of adverse influenza outcomes. IVE will be estimated against laboratory-confirmed influenza, influenza-like illness, hospitalization, ICU admission, and mortality.

Population: Within Denmark, Finland, and Sweden, we will include all individuals aged 65 years and above, and adults at high risk below 65 years of age, who are known residents.

Variables: The primary outcomes are laboratory-confirmed influenza (types A and B, combined and separately), influenza hospitalization, and influenza-related death. The secondary outcomes are hospitalisation for influenza-like-illness, hospitalisation for respiratory infections, ICU admission, and all cause-mortality. Covariates include demographic characteristics and comorbidities.

Data sources: Nationwide demography- and healthcare registers within each participating country.

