9.5 Study size

Below we describe key target group sizes, vaccination coverage and recorded influenza infection incidences in the three Nordic countries for the 2023-2024 season. This provides a good indication of the possible study size for the 2024-2025 season. We expect to include at least 3.2 million individuals who are included in the key target groups for seasonal influenza vaccination across the 3 Nordic countries.

In Denmark, the total population of individuals aged 65 years and older, along with the population at increased risk below 65 years of age, consisted of 1,211 million and 554,780 individuals, respectively, as of 20 December 2024. (39) From 1 October 2024 to 20 December 2024, influenza vaccination coverage in these target groups was 75.6% and 29.2%, respectively. (39) As of 13 January 2025, there were 700 confirmed cases of influenza, including 414 hospitalisations, in older adults above 65 years. (40)

In Finland, the total population of individuals aged 65 years and older was 1,315 million with a vaccine coverage of 61% during the 2023-2024 season. The population at increased risk aged between 18 and 64 years comprised of 0,52 million individuals. The influenza A incidence was 65.5 per 10,000 person-years, and influenza A hospitalisation incidence was 5.4 per 100,000 person-years. As of 20 January 2025, there were 3224 confirmed cases of influenza in the Finnish population, including 81 hospitalisations due to influenza in adults aged 65 years and above. (41,42)

In Sweden, the total population of elderly 65 years and above in the four regions under study comprise of 280,000 individuals, with national influenza vaccination coverage of 69% in the 2023/2024 season. (43)

We will utilize all available data to us from the countries' nationwide registers (Denmark and Finland), and regional data sources (Sweden). The statistical power of our proposed study will be reflected in the 95% CI of the effectiveness estimates. We expect to have robust statistical precision for the most widely used influenza vaccine brands within the current season. (44,45)

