The test-negative case-control (TNCC) study design is a variant of the case-control method specifically developed for evaluating VE. (48) Due to unavailability of test negatives data in Finland and Sweden, we will conduct a TNCC study on Danish data only. In this approach, cases are individuals who test positive for influenza, while controls are those who test negative. The TNCC design offers several methodological strengths. It reduces bias from healthcare-seeking behaviour, as both cases and controls sought care and allows for efficient VE estimation during the influenza season. However, the TNCC design also has important limitations. It assumes that influenza vaccine does not affect the risk of other, non-influenza respiratory infections. (48) The design may be subject to bias if cases and

controls differ in disease severity. (49) Moreover, as the use of electronic healthcare records, including register-based data, for identifying cases and controls might cause bias (e.g., misclassification), and active enrolment of study participants is ideal in the TNCC design. (50) However, this increases the cost of the TNCC studies and limits its practicality to estimate VE against rare outcomes. Since a core assumption of the TNCC design is similar healthcare seeking behaviour among those who get tested, there is potential for selection bias if testing practices vary by vaccination status or other patient characteristics.

In the Danish population of individuals who were PCR-tested for influenza during the 2024–2025 season, we will employ a TNCC design to estimate the vaccine effectiveness against influenza infections during the 2024–2025 influenza season. We will exclude negative tests within 7 days of a previous negative test and within 21 days of a subsequent positive test. All tests within 90 days of a previous positive test will be excluded as these likely represent the same episode. Individuals can contribute with a maximum of one negative PCR test, which will be selected at random.

Patients will be considered vaccinated if they received an influenza vaccine at least 14 days before the PCR sample date. Patients will be considered unvaccinated if they have not received the influenza vaccine on the PCR test date or if they have received the influenza vaccine within two weeks before the PCR test date.

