Logistic regression models will be used to estimate the odds ratio (OR) with 95% CIs. Our main estimate of interest is the vaccine effectiveness defined by $(1-OR) \times 100\%$. The models will be adjusted for age, sex, region of residency and comorbidities. We will assess whether the frequency of testing differs between vaccinated and unvaccinated groups during the season, since differential testing could bias VE estimates. The testing frequency will be visualized in a plot stratified by month and vaccination status.

Prior event rate adjustment

A difference-in-differences approach in the form of prior event rate ratio (PERR) adjustment exists for evaluating healthy vaccinee bias for influenza outcomes. (51) The PERR method is built on the assumption that any differences in event rates unrelated to vaccination between vaccinated and unvaccinated individuals can be observed in the period before vaccination is available. This can be implemented using the pairwise version of PERR. (51)

The matching and censoring criteria from the main TTE analysis will be applied. As before, the day the seasonal vaccine dose was administered within each matched pair will serve as the index date for both individuals. For each individual within a matched pair, the pre-vaccination period will be the start of the 2024/2025 influenza season (1 October 2024) until the index date and the post-vaccination period will start on day 14 following the index date. We will identify individuals who ultimately receive a seasonal influenza vaccine (“future vaccinated”) and those who remain unvaccinated (“future unvaccinated”), evaluated at the end of the studied period or on the date of the outcome. Both groups will have the number of outcomes and the amount of person-time measured in the pre-vaccination period (to establish baseline event rates) and in the post-vaccination season (to assess post-vaccination event rates).

The outcome under study is influenza-related hospitalization. Given that influenza hospitalization may be less frequent at the start of the influenza season, we will assess whether sufficient events occur in the pre-vaccination period to produce stable estimates.

We will employ the pairwise version of PERR, which effectively compares the ratio of (current vs. pre-vaccinated) event rates in the vaccinated group to the ratio of (current vs. pre-vaccinated) event rates in the unvaccinated group. Formally:

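### The Danish test-negative model has no term for calendar time of the test, so its VE is biased downward when tests are sampled over the whole season

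*Protocol*

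**What the plan says.** Section 9.8 (Test-Negative Case Control design) takes its sample from the whole 2024-2025 season: "In the Danish population of individuals who were PCR-tested for influenza". A person counts as vaccinated when the dose was given at least 14 days before the sample. A person counts as unvaccinated if not vaccinated by the test date, or "if they have received the influenza vaccine within two weeks before the PCR test date". Each person contributes at most one negative test, chosen at random.

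The analysis is stated as follows: "Logistic regression models will be used to estimate the odds ratio (OR) with 95% CIs", with VE equal to one minus the odds ratio, and "The models will be adjusted for age, sex, region of residency and comorbidities". Calendar month appears only in description: "The testing frequency will be visualized in a plot stratified by month and vaccination status", with a similar table or graph under Testing frequency.

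Section 9.3 says that Danish vaccination starts on 1 October. Section 9.5 says that by 20 December "influenza vaccination coverage in these target groups was 75.6% and 29.2%, respectively", for those aged 65 and over and for the under-65 risk groups.

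**The concern.** Exposure in this design depends on the date of the test. Nobody vaccinated in the programme can count as vaccinated before 15 October, and coverage then climbs steeply. Influenza comes later: the prior-event-rate text in Section 9.8 itself expects few influenza hospitalisations at the start of the season. Test date is thus linked to both exposure and case status, and age, sex, region and comorbidity do not remove that link. Early negatives are nearly all unvaccinated and have almost no cases from the same weeks beside them.

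The main cohort does not share the problem, because it matches on the day of vaccination. Section 9.8 introduces the test-negative study to evaluate bias from healthcare-seeking and healthcare access in that cohort. If the check is pulled down by timing alone, a gap between the two could be read as evidence against the primary estimate.

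**Working it through.** The protocol gives no expected VE or sample size for this analysis, so there is no figure to reproduce. The check asks what the stated model returns when the true VE is known.

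**Inputs from the protocol.** Plateau coverage c is 0.756 (65+) or 0.292 (risk groups). Vaccination starts on 1 October, with a 14-day lag. Data run to the example end date of 1 March, which is 31+30+31+31+28 = 151 days.

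**Assumed.** The true odds ratio is R = 0.6 (VE 40%). Weekly positivity, shape of uptake and test volume are not in the protocol.

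**Simplified hand calculation.** Let a share f of negatives be sampled before anyone counts as vaccinated, and let the other negatives and all cases come after coverage has reached c.

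- Vaccination odds in cases: R·c/(1-c)
- Vaccination odds in pooled controls: (1-f)·c/(1-c+c·f)
- Pooled odds ratio: R × (1-c+c·f)/[(1-c)(1-f)]

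Example: negatives spread evenly over 151 days, and coverage jumping to its plateau on 15 October. Then f = 14/151 = 0.093. In 65+ the multiplier is (0.244+0.070)/(0.244×0.907) = 1.42, so the odds ratio is 0.85 and VE is 15%.

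| f | VE, 65+ | VE, risk groups |
|---|---|---|
| 0.05 | 27% | 36% |
| 0.10 | 13% | 31% |
| 0.20 | -22% | 19% |
| 0.30 | -65% | 4% |

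Estimated VE reaches zero when the multiplier is 1/0.6 = 1.667, that is at f = 0.667(1-c)/[c+1.667(1-c)]. This is 0.163/1.163 = 0.14 in 65+ and 0.472/1.472 = 0.32 in the risk groups.

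**Week-by-week calculations, gradual uptake, 22 weeks, true VE 40%.** In each week a fraction c_w of controls and R·c_w/(R·c_w+1-c_w) of cases are vaccinated. Peak positivity was 20% or 30%, and test volume flat or rising.

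- 65+, fast, medium or linear uptake over about 11 weeks, peak in weeks 16 to 18: -62% to +15% over 12 scenarios, of which 8 were below zero and 4 above.
- 65+, 14-day lag, uptake over 5, 8 or 11 weeks: -82% to +6%.
- Risk groups, same lagged set-up: -3% to +28%.

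**Half-month periods, true VE 35%** (the Danish 65+ estimate against H1N1pdm09 cited in Section 7), peak positivity 30%.

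- 65+, flat number of negatives: -55% to -121%.
- 65+, negatives concentrated late in the season: -8% to -44%.
- Risk groups, flat: +3% to -23%.
- 65+, flat, tests only from mid-November: +24% to -13%.
- 65+, tests only from mid-December: 25% to 34%.

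**With time in the analysis.** Within a week the control odds are c_w/(1-c_w) and the case odds are R times that, so every weekly odds ratio equals R. The Mantel-Haenszel estimate over weeks or half-months returned the true VE in every scenario.

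**The case against.** The analysis is supplementary and Danish only. It feeds no primary, brand-specific or pooled estimate. Negative control outcomes and testing frequency address the same healthcare-seeking bias, and the protocol plans to triangulate. All of that stands and limits the severity. A separate analysis plan could add a time term, but the protocol's list is explicit and does not contain one.

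The size depends on curves that the documents do not give. The only anchored figures are the two coverage values and the start date. This also stands.

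Three stronger readings are tempting but unsupported.

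- **The VE will come out at or below zero.** It can, but that depends on the scenario. Several 65+ results are positive, and a late sampling window leaves little bias.
- **Sampling all tested Danes makes the timing bias worse.** The opposite holds for this mechanism: lower coverage gives less bias, as the risk-group figures show. It is also unclear that the sample goes beyond the target groups, since Section 9.2 defines the study population as those groups.
- **Coding days 0 to 13 as unvaccinated is an error in itself.** It does lower the unadjusted VE; excluding those samples raised it by about 12 to 20 points. But with stratification by day of test, the recoded data returned 40.0% in all 12 scenarios, provided there is no protection before day 14.

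**Conclusion.** The point holds in this form: as written, the test-negative VE is biased downward because the model omits calendar time of the test. The direction follows from the protocol's own facts, namely zero counted coverage until mid-October, a steep rise afterwards, and influenza expected later.

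For a true VE of 40%, an illustrative size is roughly -80% to +15% in 65+ and -3% to +28% in the under-65 risk groups. These ranges rest on assumed uptake, positivity and test volume; they are neither bounds nor forecasts. Nothing here shows the primary cohort estimate to be wrong. Severity: should be fixed.

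**What to change.** Add calendar week of sampling to the logistic model, as categories or a spline, or use conditional logistic regression within week. The sample date is already held in the Danish Microbiology Database.

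Two optional additions: report the analysis separately for 65+ and for the 18-64 risk groups, so that it lines up with trials 1 and 2; and exclude samples taken 0 to 13 days after vaccination as a sensitivity analysis.

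The cost is one extra model term and slightly wider intervals, because weeks with almost no cases then contribute little.

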9. RESEARCH METHODS

9.1 Study design

We will take advantage of the unique nationwide register-data available to us, and construct country-specific cohorts with individual-level information on dates of vaccination and dates of effectiveness endpoints together with relevant covariate information. All Nordic residents are assigned a unique personal identifier at birth or immigration, enabling linkage between register data. Nordic countries have universal and tax-financed healthcare systems and reporting to national registers is mandatory, providing near-complete follow-up of all residents over time.

The study period will start on 1st October 2024 in the three countries. This study start date corresponds to the start of the seasonal influenza vaccination program in the three countries. The study period will end on the last date of data availability at time of analyses during spring 2025.

The study design will build on our previous work with Covid-19 vaccination effectiveness in the Nordic countries (19,20). We will utilize a cohort design in a target trial emulation (TTE) framework to estimate both relative and absolute effects. The evaluations in 65+-yr-olds and risk groups 18-64-yr-olds will be designed as two separate target trial emulations. Key components of the specification and emulation of the pragmatic target trials of the effectiveness of brand-specific seasonal IVE using Nordic nationwide register data are included below in Table 1.

Table 1. Target trial emulation framework

Protocol	Target Trial Specification	Target Trial Emulation
Eligibility criteria	
 • Individuals 65+-years-of-age (trial 1) • Individuals in risk groups 18-64-yr-of-age (trial 2) • Have a permanent residency in Denmark, Finland, or Sweden at start of study period 	Same as for the target trials.
Treatment strategies	Vaccination with any of the following influenza vaccines InfluvacTetra, VaxigripTetra, FludTetra, FluarixTetra or Efluelda Tetra, October 1, 2024 to January 31, 2025 vs vaccination with placebo in the same period.	Same as for the target trials except vaccination with placebo is replaced by no vaccination with any of the vaccines under study.

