$$PERR = \frac{\frac{Event\ Rate_{Vaccinated,current}}{Event\ Rate_{Vaccinated,pre-vaccinated}}}{\frac{Event\ Rate_{Unvaccinated,current}}{Event\ Rate_{Unvaccinated,pre-vaccinated}}}$$

This ratio-of-ratios approach aims to adjust for pre-existing differences between those who choose vaccination and those who do not.

We will use Poisson regression to estimate event rates during the pre-vaccination and current periods. We will report point estimates and 95% confidence intervals for the PERR-adjusted measure of VE (1-PERR). The precision of these estimates will depend on the number of events in the pre-vaccination period. With high vaccine uptake and the vaccination occurring early in the start of the influenza season, the pre-vaccination period may produce fewer events. PERR results will be interpreted carefully and considered alongside the main matched cohort analyses and other supplementary analysis.

Negative control outcomes (NCO)

To evaluate the possible residual confounding in analysis of influenza vaccine effectiveness, we will analyse the association between influenza vaccination and the following negative control outcomes (NCO) in our main study design: Lower back pain (ICD10: M543-M545), clavicle fracture (ICD10: S420), and diverticulitis (ICD: K57).

Analysing negative control outcomes is a way to assess residual confounding. (70) Negative control outcomes such as lower back pain, clavicle fracture, and diverticulitis are conditions biologically unrelated to both vaccination and influenza. Any association between influenza vaccination and these outcomes would suggest residual confounding e.g. by healthcare seeking behaviour which could bias VE estimates. If no associations are found, it supports the validity of the primary analysis. Significant associations would indicate confounding that requires further adjustment or caution in interpretation. This relies on the assumption that the association between influenza vaccination and the negative control outcome is subject to the same confounders as the association between influenza vaccination and the influenza outcomes. Including negative control outcomes strengthens the study's credibility.

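### The PERR check takes its baseline mainly from later vaccinees and applies it to events mainly from earlier ones, so it is unbiased only under an unstated assumption that both are confounded alike

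*Protocol*

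**What the plan says.** All of this is in the protocol, mostly under Prior event rate adjustment in Section 9.8.

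- **Baseline window.** For each member of a matched pair, "the pre-vaccination period will be the start of the 2024/2025 influenza season (1 October 2024) until the index date".
- **Current window.** "the post-vaccination period will start on day 14 following the index date".
- **Range of index dates.** Table 1 in Section 9.1 allows vaccination from "October 1, 2024 to January 31, 2025".
- **Estimator.** "We will employ the pairwise version of PERR, which effectively compares the ratio of (current vs. pre-vaccinated) event rates in the vaccinated group" with the same ratio in the unvaccinated group. The printed formula has one event rate per arm and period. On the model, the text says "We will use Poisson regression to estimate event rates during the pre-vaccination and current periods". No term for index date or calendar time is given.
- **Rationale.** PERR is offered as a way to evaluate healthy vaccinee bias. It assumes that differences unrelated to vaccination "can be observed in the period before vaccination is available".
- **Caveats given.** The outcome (influenza hospitalisation) may be rare early in the season, and early, high uptake may leave few baseline events. Both caveats concern stability and precision.

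**The concern.** The length of the baseline depends on when the person was vaccinated. A pair indexed on 1 October has none, and a pair indexed on 31 January has 122 days. Early baselines also fall where the protocol itself expects few influenza hospitalisations. Baseline events therefore come disproportionately from late pairs. Current-period events come mainly from early pairs, which are more numerous and are followed through the wave.

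A pooled ratio of ratios then uses the baseline imbalance of one group to correct the current imbalance of another. That cancels confounding only if the two groups are confounded to the same degree.

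The choice of 1 October contributes to this. The stated rationale needs a period before vaccination is available, yet Section 9.1 says of 1 October: "This study start date corresponds to the start of the seasonal influenza vaccination program in the three countries". (Section 9.3 gives 15 October for Sweden.) There is thus no common baseline that ends before vaccination begins.

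At stake is the value of PERR for triangulation. It could appear to confirm or contradict the cohort result because of who supplies the baseline events.

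**Working it through.** The protocol gives no PERR figure, event count or bias estimate, so there is nothing to reproduce. The check is an expected-value calculation.

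**Formula.** Let s be the index-period stratum, c_s the vaccinated/unvaccinated rate ratio in the absence of vaccination, p_s the share of unvaccinated members' pre-period events that comes from s, q_s the same share for the current period, and θ = 1 - VE. The two members of a pair share the same windows, so person-time very nearly cancels:

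PERR = θ × (Σ q_s c_s) / (Σ p_s c_s)

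This equals θ if c_s is constant or if the two sets of shares coincide. The unadjusted ratio is θ × Σ q_s c_s.

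**Input from the protocol.** Section 9.5, on Danish people aged 65+ and at-risk people below 65: "From 1 October 2024 to 20 December 2024, influenza vaccination coverage in these target groups was 75.6% and 29.2%, respectively".

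**Assumptions, not in the protocol.** Shape of uptake before and after 20 December, a bell-shaped wave peaking in January or early February, data to 1 March, true VE 40% (θ = 0.6), and the values of c_s.

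**Shares.** With a late stratum defined as index dates from 1 December, late vaccinees are about 8-13% of vaccinees. They supply about 74-89% of pre-period events but 11-25% of current-period events.

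**Results at the extremes of those shares:**

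| Ratios early/late | Shares q, p (late) | Unadjusted VE | PERR VE |
|---|---|---|---|
| 0.8 / 1.0 | 0.11, 0.89 | 1 - 0.6×0.822 = 50.7% | 1 - 0.6×0.822/0.978 = 49.6% |
| 0.8 / 1.0 | 0.25, 0.74 | 1 - 0.6×0.850 = 49.0% | 1 - 0.6×0.850/0.948 = 46.2% |
| 1.0 / 0.8 | 0.11, 0.89 | 1 - 0.6×0.978 = 41.3% | 1 - 0.6×0.978/0.822 = 28.6% |
| 1.0 / 0.8 | 0.25, 0.74 | 1 - 0.6×0.950 = 43.0% | 1 - 0.6×0.950/0.852 = 33.1% |
| equal | any | depends on c | 40% |

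**Sensitivity.** A second set of scenarios used a cut at 16 November, coverage of 75.6%, 61% or 29.2%, wave peaks from 1 January to 8 February, and ratios of 0.7 and 1.0.

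- *Controls reusable.* Late vaccinees were 10-29% of vaccinees, with 52-99% of pre-period and 9-51% of current events. PERR VE was 46-56% (0.7 early, 1.0 late) against 49-56% unadjusted. Reversed, it was 19-34% against 42-49%.
- *Controls used once, 75.6% coverage.* The mismatch shrinks because controls run out. The latest fifth of pairs gives 44-77% of pre-period and 29-37% of current events, and PERR VE is 42-49% or 29-38%.
- *Stratified.* PERR computed within the early and late strata returned 40% throughout. This is by construction, since c_s was constant within each stratum.

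**The case against.** **The premise is not in the protocol.** Bias needs confounding that differs by vaccination date. A reader might take Table 8 as evidence of this, but that table concerns the propensity to be vaccinated, not its timing. Pairs are also matched on age, sex, region and comorbidity. This stands: the bias is conditional, and the ratios above are illustrative.

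**PERR need not be worse than no adjustment.** This also stands. With 0.8/1.0, PERR under-corrects but lies slightly nearer 40% than the unadjusted figure. Only the reverse pattern adds bias.

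**A reader might infer that baseline events come almost only from a few late vaccinees.** Neither the documents nor the range of scenarios supports that. The late share falls to 44% with very high uptake and controls used once. The argument needs only unequal shares.

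**The word pairwise may already cover this.** Its exact meaning sits in a cited source, and model terms could be in an analysis plan or the R scripts. In part this stands. But the printed formula and its description are group rates, so label and formula need reconciling. A conditional pairwise Poisson fit with one common period effect, at 61% or 29.2% coverage, reduced the bias but still missed 40% in nearly all scenarios (41-48% or 23-39% under the 0.7/1.0 ratios).

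**Imprecision dominates.** Section 9.5 reports 414 Danish hospitalisations above 65 by 13 January. If late vaccinees are 8-13% of 75.6%, they are 6.0-9.8% of that population, or about 25-41 events at average risk, even if all preceded vaccination. With that many events per arm, the SE of the baseline log ratio is √(2/41) to √(2/25), or 0.22-0.28, a 95% factor of about 1.5-1.7. The bias factors above are 0.84-0.90 and 1.12-1.19. So random error probably exceeds the bias, and the protocol already promises careful interpretation. But that caution addresses width only; it does not warn that the centre may be shifted.

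**Conclusion.** The point holds in conditional form. As written, PERR weights index dates differently in its baseline and current parts. It therefore rests on an assumption the protocol never states: that the baseline vaccinated/unvaccinated ratio does not depend on when people were vaccinated. If it does depend on timing, PERR can under-correct (46-50% against 49-51% unadjusted, true VE 40%) or add bias (29-33% against 41-43%). These sizes rest on assumed uptake, epidemic curves and ratios. The direction of the mismatch did not depend on them: late pairs had the larger share of baseline events in every scenario with late pairs.

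Two stronger conclusions are not supported. The documents do not show that PERR will be biased, because they are silent on confounding by timing. Nor is the primary VE touched, since PERR is one of several supplementary analyses. This is a minor-to-moderate, cheap improvement to one part of the triangulation.

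**What to change.** 1. Fit the Poisson model stratified by index period, for example October, November and December-January. Include stratum-by-period and stratum-by-vaccination terms, with one common vaccination-by-period term as log PERR. Each stratum's baseline ratio then corrects only its own current ratio, and strata without baseline events contribute nothing.
2. Reconcile the pairwise label with the printed formula, so that text and model describe the same estimator.
3. State the assumption about early and late vaccinees as a source of bias, separately from precision. State also that the result speaks mainly for the index dates that supply baseline events.
4. Show the main-analysis VE for those same index dates beside the PERR estimate. The pooled PERR may stay for comparison.

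**Cost.** A few terms in the common R script and a modestly wider interval: in the scenarios with the 1 December cut, the standard error of log PERR rose by only about 2-13%, because pooled precision already rests on the same few late baseline events. The check will openly cover mainly later vaccinees. Any difference in confounding within a stratum remains uncorrected.
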